#### 9.3.3. Potentially Clinically Important Laboratory Values

Criteria for potentially clinically important laboratory values are listed in Table 5 below.

Note that combination of values need to be measured on the same day.

The number and percentage of participants with postbaseline liver specific function test values that meet each of the above criteria will be presented at each scheduled visit by treatment groups. Participants with potential DILI events will also be listed.

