8.3.7. Laboratory Assessments

See Table 10 for the list of clinical laboratory analytes to be performed and Table 3 for the laboratory assessment visit schedule. A central laboratory will perform all clinical laboratory assessments for safety (ie, blood chemistries, hematology assessments, urinalysis, inflammation markers, and lipid panel).

Additional testing may be required by the sponsor based on emerging safety data. All Protocol-required laboratory assessments must be conducted in accordance with the Laboratory Manual and Table 3. Information regarding collection, processing, and shipping of samples for laboratory assessment is provided in the Laboratory Manual.

Clinically significant abnormal laboratory findings are those that are not associated with the underlying disease, unless judged by the investigator to be more severe than expected for the participant's condition. All laboratory tests with values considered clinically significantly abnormal during participation in the study or within 4 weeks after the last dose of study drug should be repeated until the values return to normal or baseline or are no longer considered clinically significant by the investigator or medical monitor.

If screening laboratory assessments are performed more than 30 days before Day 1, then the tests must be repeated and eligibility confirmed before study drug administration on Day 1. Laboratory sample collection on Day 1 must be performed before study drug administration.

See Section 9.1 for information regarding laboratory abnormalities that should be recorded as an AE in the eCRF.

Table 10: Required Laboratory Analytes	Table 10:	Required Laboratory Analytes
--	-----------	-------------------------------------

Chemistry	Hematology	Urinalysis	Serology/Infection	Pregnancy testing

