8.6. Unscheduled Visits

Unscheduled visits may occur at any time at the investigator's (or designee's) discretion, and appropriate clinical and laboratory tests may be performed, as clinically indicated.

If there is a potential clinically significant abnormality in hematology or chemistry assessments (particularly in platelet count) during the study, an unscheduled visit within the following week should occur to repeat laboratory assessments (further details are provided in Table 7 and Section 8.3.7). See Section 6.5.1 for instructions on dose interruption and restart. The investigator must inform and consult the sponsor (or designee) with any hematological abnormality.

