#### 9.3.2. Laboratory Value Summaries

All test results and associated normal ranges from central laboratories will be reported in SI units. All tests with numeric values will have a unique unit per test. Any laboratory test results and associated normal ranges from local laboratories will be converted to SI units.

When there are multiple laboratory nonmissing values for a participant's particular test within a visit window, the laboratory value with the smallest laboratory sequence number will be used in by-visit summaries.

For test results that will be summarized with available normal ranges, the number and percentage of participants with laboratory values being low (but never high), normal, high (but never low), and both low and high will be calculated for each test. This shift summary will be produced for each test. The denominator for the percentage calculation will use the number of participants in the baseline category (ie, low, high, normal, missing) as the denominator for the percentage in each of the categories during the study.

Severity grades will be assigned to laboratory test values based on the numerical component of CTCAE v5. Shift tables will also be presented showing change in CTCAE grade from baseline to the worst grade postbaseline. Separate summaries for abnormally high and abnormally low laboratory values will be provided when the laboratory parameter has both high and low grading criteria. The denominator for the percentage calculation will be the number of participants in the baseline category. The number of participants who experienced worsening of laboratory abnormalities will be summarized by maximum severity.

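### The by-arm liver-criteria table counts participants only at scheduled visits, so a criterion first met at an unscheduled retest can be missing and the number of participants affected per arm cannot be read from it.

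*SAP*

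**What the plan says.** SAP 9.3.3 covers potentially important laboratory values, and its visible text runs on into the liver criteria that the table of contents places in 9.3.4. It plans a count and percentage of participants whose postbaseline liver tests "that meet each of the above criteria will be presented at each scheduled visit by treatment groups". For combined criteria it adds: "Note that combination of values need to be measured on the same day". It ends: "Participants with potential DILI events will also be listed".

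SAP 9.3.2 sets the rule for visit windows that contain more than one result: "the laboratory value with the smallest laboratory sequence number will be used in by-visit summaries". The same section also provides a worst-value display for graded analytes: "Shift tables will also be presented showing change in CTCAE grade from baseline to the worst grade postbaseline".

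Protocol 8.6 describes what happens when a result looks abnormal. "If there is a potential clinically significant abnormality in hematology or chemistry assessments (particularly in platelet count) during the study", then "an unscheduled visit within the following week should occur to repeat laboratory assessments". Protocol 8.3.7 adds that results judged clinically significantly abnormal "should be repeated until the values return to normal or baseline or are no longer considered clinically significant by the investigator or medical monitor".

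**The concern.** The protocol places the follow-up of a rising liver test outside the visit calendar, while the SAP counts liver criteria on the visit calendar. Results from retests are collected, but the planned by-arm table has no evident place for them.

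Two things follow. First, a participant whose scheduled value is raised but below a cut-off, and who crosses it at the retest, may not appear in the table. The same holds for one who reaches a higher category or completes a combined criterion there. Second, even with scheduled data alone, per-visit counts do not identify people. One participant at each of two visits may be two participants or the same one twice.

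At stake is the plainest liver-safety statement the study can make: how many participants in each dose group and on placebo ever met each criterion. Where cases are few, one omission can decide whether an arm shows zero.

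**Working it through.** The documents state no figure on this point, so there is nothing to reproduce. The check asks whether a retest done as Protocol 8.6 directs could enter a by-visit table.

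**Inputs**
- Retest timing: 1 to 7 days after the abnormal result (Protocol 8.6).
- Placebo-controlled visits: Weeks 2, 4, 6, 8, 12 and 16, each ±3 days (Protocol Section 1 and Table 3).
- Open-label extension (OLE) visits: Weeks 18, 20, 22 and 24, then every 4 weeks from Week 28 to Week 52, ±3 days. That is 4 + 7 = 11 visits.
- Long-term extension (LTE) visits: Weeks 60, 68, 76, 84, 92 and 100, ±7 days. That is 6 visits.
- Group size: about 50 (SAP 3.1).
- Assumption: the SAP's analysis windows are not visible. Two readings were tried, the protocol's visit windows and windows cut at the midpoint between visits.

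**Count under the protocol windows.** Pair each visit with each of the 7 possible retest days. With a ±3-day window, retest days 1 to 3 fall in the window of the visit that triggered them and days 4 to 7 fall outside it.

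| Period | Pairs | In triggering visit's window | In next visit's window | In no window |
|---|---|---|---|---|
| Placebo-controlled | 6 × 7 = 42 | 6 × 3 = 18 | 0 | 6 × 4 = 24 |
| OLE | 11 × 7 = 77 | 11 × 3 = 33 | 0 | 11 × 4 = 44 |
| LTE (±7 days) | 6 × 7 = 42 | 6 × 7 = 42 | 0 | 0 |

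The next visit is at least 14 days away and its window opens no earlier than day 14 − 3 = 11, so no retest in the first 7 days reaches it.

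**Count under midpoint windows.** The shortest gap is 14 days, so its midpoint is day 7. All 42 + 77 + 42 = 161 pairs fall in the triggering visit's window.

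**Applying the selection rule.** A retest that falls in no window has no scheduled visit to be reported under. A retest in the triggering visit's window competes with the scheduled value. If sequence numbers follow time and the scheduled value is present, the scheduled value has the smaller number and is used. Under either reading the retest does not enter the by-visit count. This takes the liver table to be a by-visit summary under SAP 9.3.2, which its layout suggests but the text does not say.

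**What is lost.** If the scheduled value that prompted the retest already meets the criterion, it is counted. What can be lost is a criterion, combination or higher category first met at an unscheduled draw. How often that happens cannot be derived from the documents.

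**Scale.** One participant in a group of 50 is 1/50 = 2.0 percentage points. For assumed true rates p of 0.5%, 1%, 2% and 4%, the chance of at least one case in a group is 1 − (1 − p)^50 = 22%, 40%, 64% and 87%. At the lower rates a group will often have no case or very few, so a single omission can change how it reads. These rates are illustrative and do not estimate how many cases would be missed.

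**The case against.** The strongest reply is that the study would see these cases by other routes.

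- **Graded shifts.** The worst-postbaseline CTCAE shift tables and the summary of worsening by maximum severity (SAP 9.3.2) are by participant and are not stated to be limited to scheduled visits. A single-analyte peak at a retest has a by-group route there. This stands. Those tables do not show a transaminase rise together with a bilirubin rise, nor cut-offs that are not grade boundaries.
- **Adverse events.** Clinically meaningful laboratory abnormalities are adverse events under Protocol 9.1, and SAP 9.2.2 counts participants with treatment-emergent events by group. This stands, but it counts reported terms, not criteria met.
- **The listing.** Participants with potential DILI events are listed individually. A reader might infer that the listing inherits the scheduled-visit limit. The text does not say so, and a same-day combination found at a retest may well appear there. The listing still gives no n (%) by arm, and its data source is unstated.
- **What cannot be seen.** The contents of Table 5, the opening of 9.3.4 and the list of displays are not visible, so an any-time row may already exist. This stands as a limit on the point.
- **The same-day rule.** A reader might take it as a second defect. It applies only to combinations, and ALT, AST and total bilirubin share one chemistry panel (Protocol Table 10), so a full-panel draw gives same-day values. Requiring concurrence is a defensible analytic choice, and a looser rule could flag unrelated elevations.
- **Weight.** Laboratory data are descriptive, with no formal group comparisons planned (Protocol 10.4.3). This stands and keeps the point modest.

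**Conclusion.** The point holds in a limited form. In the visible text, the only by-arm count of the liver criteria is per scheduled visit. Such a count can leave out a participant who first meets a criterion at an unscheduled draw, and it does not give the number of participants affected. The gap matters most for combined criteria, which no other visible by-arm summary covers.

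The number of participants involved is unknown; each is 2 percentage points of a group of about 50. The conclusion assumes that sequence numbers follow time, that the liver table follows the by-visit rule, and that the hidden displays hold no any-time row.

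Two stronger readings are not supported. One is that liver cases found at retests go unreported: shift tables, adverse event counts and the listing all remain open to them. The other is that the loss can be sized by dividing an assumed episode length by the visit spacing. That ratio describes episodes during which no scheduled draw happened to fall. Most of these would have no draw at all, so no reanalysis of collected data could recover them. Long-spacing examples would also misdescribe the placebo comparison. From baseline to Week 16, four of the six gaps between chemistry draws are 14 days, and the 8-week spacing belongs to the LTE, which has no placebo group.

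**What to change.** In SAP 9.3.3/9.3.4, keep the per-visit table and add, for each period and treatment group, n (%) of participants who meet each liver criterion at any postbaseline time, using all scheduled and unscheduled values. Keep the same-day rule for combinations. State that the listing of potential DILI events also draws on all values. If the hidden displays already contain such a row, a sentence in the text saying so is enough.

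One detail needs wording. SAP 4.1.3 gives participants on 75 mg throughout a safety baseline in the OLE that dates from before the placebo-controlled period. The any-time count should therefore be bounded by the dates of each period, as SAP 9.2.1 does for treatment-emergent events, so that earlier results are not counted again.

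The cost is a few lines of SAP text and one row block in a descriptive safety table. It needs no new data and does not touch the primary analysis or error control.

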### 9.4. Vital Signs

Values at each scheduled visit, change, and percentage change from baseline for vital signs, including systolic blood pressure, diastolic blood pressure, pulse, respiratory rate, and body temperature will be summarized descriptively.

Normal ranges for vital sign values are defined in Table 6. For participants exhibiting vital sign abnormalities, the abnormal values will be listed along with their assigned treatment group. Alert vital signs are defined as an absolute value outside the defined normal range and percentage change greater than 25%. Note that the definition of alert vital signs does not apply to body temperature. The abnormal values for participants exhibiting alert vital sign abnormalities will be listed.

## 9.5. Electrocardiograms

Twelve-lead ECGs including PR, QT, QRS and QTcF intervals will be obtained for each participant during the study. Values at each scheduled visit, change, and percentage change from baseline will be summarized for each ECG parameter. Baseline will be determined as the average of all nonmissing values before the first administration of INCB054707 or placebo.

Normal ranges for ECG values are defined in Table 7. ECG values will also be considered abnormal if the absolute percentage change from baseline is more than 25% (30% for QRS interval). Participants exhibiting ECG abnormalities will be listed with study visit and assigned treatment group. Abnormal values for participants with alert ECG values, defined as both the absolute value and the percentage change from baseline being outside normal ranges, will be identified and listed. Outliers of QT and QTcF values, defined as absolute values > 450 millisecond, > 500 millisecond, or change from baseline > 30 millisecond, will be summarized.

## 10. CHANGES AND MODIFICATIONS TO THE ANALYSIS PLAN

All versions of the SAP are listed in Table 8.

#### Table 8:Statistical Analysis Plan Versions

SAP Version	Date
Original	12 OCT 2021

## **10.1.** Changes to Protocol-Defined Analyses

10.2. Changes to the Statistical Analysis Plan

Not applicable.

#### Figures

VV-CLIN-017355
